4.4 Measures

4.4.1 Measures for Primary Aims

Screener. Participants will be screened with [name] 9-item Brief Skin Cancer Risk Assessment Tool (see Inclusion Criteria above) 104. Internal and test-retest reliability compare favorably to those reported in the literature for similar items/scales 104. Participants will be required to understand English and have access to the internet via any modality (e.g., computer, smartphone) at least weekly.

Demographics. Standard demographic items used by the census will assess: sex, age/birthdate, race/ethnicity, region of residence, education, income, and employment. We will include items on web use from the Health Information National Trends Survey 121, and will inquire about family history of skin cancer.

Social Desirability. Social Desirability will be assessed using the 4-item Brief Social Desirability Scale that has demonstrated adequate internal reliability and validity among young adults 122.

Reach. We will assess eligibility and enrollment overall and by recruitment source (i.e., skin protection organizations, Google Adwords, Facebook ads, consumer research panel, word of mouth) over 12-18 months in order to assess reach/potential generalizability. Sources will be tracked by placing a unique identifying pixel in each of our authorized web ads so that we know when an individual referred from a pre-specified source accesses the study website. Additionally, we will query participants as to how they found out about the study to identify informal word of mouth diffusion (e.g., unpaid study Facebook page, earned media). The number of individuals who click on the web ads, access the study homepage, complete a screening form, are eligible/ineligible, and use the website without enrolling will be assessed. Organizational sources will be monitored and queried as to strategies (i.e., posting the study URL on their website, additional promotion) used to encourage individual participation. As we have previously, we will use Google Analytics to observe user characteristics and behavior in aggregate in terms of internet source including diffusion via word of mouth, geographic location, technology used (i.e., mobile or not), eligibility/enrollment rates, and so on. We will ask organizations to set up or allow us to set up a Google Analytics "goal" to assess such user characteristics and behavior in terms of individuals accessing the study ad from within the organization's website. We will also query organizations about their number of users/members and website views if they are monitoring these.

Efficacy. Skin cancer-related behavioral outcomes will initially be assessed at baseline and 3 months later. They will also be assessed within UV4.me2 via behavioral tracking. We will assess sun protection (e.g., sunscreen use, clothing, shade) and UV exposure (e.g., sunburns, intentional/incidental sun exposure, indoor tanning) using items adapted from Glanz and colleagues and Ingledew and colleagues that our team has cognitively tested and assessed psychometrically with young adults 123-125. Sunburns, indoor tanning, and sunless tanning will be secondary outcomes since engagement in these activities is less frequent than sun exposure and protection in general. Negative effects will be defined as an increase in sunburns. Several studies have demonstrated the reliability and validity of self-report questionnaires of UV exposure and protection compared to observation and objective measures with no systematic bias identified among various populations 126-130. As indicators of quality of life, we will inquire as to the amount of perceived benefits of and barriers to UV exposure and protection 62,131-134.

4.4.2 Measures for Secondary Aims

Maintenance. Skin cancer-related behavioral outcomes (described above) will be assessed at 6 and 12 months. We will also assess maintenance of reach, intervention implementation, and cost over time.

Implementation. Using BeHealth's data management system, we will record whether, how frequently, and for how long participants logged into the interventions, how many sections are completed, use of the enhanced features, and whether these variables are associated with behavioral outcomes. Whether individuals click into the pages with discounts/free samples will be noted. Whether and when a user accesses the e-pamphlet will be noted as well. We will ask participants to give Likert ratings of their satisfaction with and perceived helpfulness of the study/intervention and selected components (e.g., the enhanced features) both from within the intervention and a one-month follow-up inquiry. The 4-item App Subjective Quality scale from the Mobile App Rating Scale will be used to assess satisfaction (a = .93) 135. We have experience using Google Analytics "goals" to track how frequently pages within modules are accessed. These implementation variables will also be linked to participant source (i.e., skin protection organizations, Google Adwords, Facebook ads, consumer research panel) when possible so that sources can be compared by participant intervention implementation.

Cost. We will assess total and incremental costs and evaluate the cost-effectiveness of the interventions. We will first estimate costs from a payer perspective, capturing the explicit resources required to deliver the program after all start-up costs (e.g., development/programming costs) have been incurred. We will also estimate costs from a societal perspective, which includes all costs, regardless of who bears them. These will include all explicit costs as well as the implicit program costs related to participant time (i.e., opportunity costs 136. We will also denote whether costs are related to research or intervention delivery. We will collect cost data using a modified version of prior cost surveys developed by RTI 137,138 and adapted by [name] for many interventions 139,140. The surveys capture all relevant labor- and non-labor-related inputs necessary to quantify costs. We will quantify participant time spent on the intervention using data from BeHealth's system and valuing participant time using age- and sex-specific wage rates, netting out research incentive payments to participants. We will quantify labor costs as program staff time (via questionnaires) valued using actual or estimated wages. Non-labor costs will be collected using program billing records and include materials/supplies used to support program activities and costs for facilities and contracted services. To evaluate the cost-effectiveness of UV4.me2 versus UV4.me and the e-pamphlet, we will combine cost estimates with effectiveness outcomes to estimate the cost per incident of UV exposure and sunburn averted.

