4.5 Compensation

Acceptability/Usability Testing. Participants who complete testing will be eligible to receive \$25 in giftcards or cash equivalent.

RCT. In addition to discounts and free samples, enrolled participants in each intervention condition will be eligible to earn the following incentives in gift-cards or cash equivalent for completing study assessments: 1 month = \$10, 3 months = \$15, 6 months = \$20, 12 months = \$25, plus a \$25 bonus for completing all time-points, and \$5 for logging into the interventions for the first time, for a possible total of \$100 throughout the year, plus a chance in a raffle for \$100 at each time-point. We chose this level of incentives to balance two issues: 1) we wanted to encourage young adults to complete the longitudinal study assessments, but 2) when the research phase is complete, individuals will not be paid for using the program (other than the discounts and free products).

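### Read literally, the plan subtracts payments for completing surveys from the value of time spent on the intervention, which understates the societal participant-time cost by about $63 per participant

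*Combined protocol and SAP*

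**What the plan says.** Section 4.4.2 (Cost) sets out a payer analysis and then "a societal perspective, which includes all costs, regardless of who bears them". On the content of the societal cost it says: "These will include all explicit costs as well as the implicit program costs related to participant time". The time in question is use of the intervention: "We will quantify participant time spent on the intervention using data from BeHealth's system". The valuation rule is "valuing participant time using age- and sex-specific wage rates, netting out research incentive payments to participants". The same section adds a labelling step: "We will also denote whether costs are related to research or intervention delivery".

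Section 4.5 describes the payments. Participants in every arm can earn "incentives in gift-cards or cash equivalent for completing study assessments": $10 at 1 month, $15 at 3 months, $20 at 6 months and $25 at 12 months. A further $25 is paid for finishing every time-point and $5 for a first login. There is also a raffle at each time-point. Section 4.5 notes that users will not be paid once the research phase is over.

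Secondary Aim 3 (Section 2.2) is to determine the costs of UV4.me and UV4.me2. Section 13.2 (Cost) reports mean and median cost for each intervention and forms cost-effectiveness ratios from between-arm differences in cost and effect.

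**The concern.** The time being valued and the payments being deducted belong to different activities. The valued hours come from the intervention's usage log, whereas nearly all of the payment is for answering follow-up surveys. A participant who is paid for a 12-month survey has given up no less time to the website.

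The payments are also transfers from the study to participants. From a societal standpoint a transfer does not reduce the opportunity cost of time, so subtracting it without entering it elsewhere takes a real cost out of the total.

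Two sets of figures are at stake: the societal cost in each arm, and the delivery cost in each arm that Secondary Aim 3 is meant to supply. Section 13.2 also uses costs to explore scale-up. A deduction for research payments would carry into that setting, where by Section 4.5 no such payments exist.

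**Working it through.** **Inputs from the documents**
- Payments (Section 4.5): $10, $15, $20, $25, a $25 bonus and $5 for first login.
- Planned follow-up (Sections 13.1 and 13.2): 1350, 1200, 960 and 768 of 1500 at 1, 3, 6 and 12 months, that is 90%, 80%, 64% and 51.2%.
- Login: 70%, the proportion of those randomised to UV4.me who accessed it in the prior trial (Section 1.0).

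**Assumptions made here**
- The 70% login rate applies to all three arms, including the e-pamphlet.
- The bonus is earned by everyone who completes 12 months. This is an upper bound, because it requires all time-points.
- Wages of $10 to $20 per hour. The documents give neither wages nor hours of use.
- The raffle is left out, because its odds are not stated.

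**Step 1. Reproduce the plan's maximum.** 10 + 15 + 20 + 25 + 25 + 5 = $100, as stated. The part tied to assessments is 100 − 5 = $95.

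**Step 2. Expected deduction per randomised participant.**
10×0.90 + 15×0.80 + 20×0.64 + 25×0.512 + 25×0.512 + 5×0.70
= 9.00 + 12.00 + 12.80 + 12.80 + 12.80 + 3.50 = **$62.90**.
Of this, 62.90 − 3.50 = $59.40 comes from assessments. With 100% login the total is 59.40 + 5.00 = $64.40. If nobody earned the bonus, it would be 62.90 − 12.80 = $50.10.

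**Step 3. Hours of use at which mean net time cost reaches zero** (deduction ÷ wage).
- $10 per hour: 62.90 / 10 = 6.3 h
- $15 per hour: 62.90 / 15 = 4.2 h
- $20 per hour: 62.90 / 20 = 3.1 h

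**Step 4. What each reading of the clause does**, for an illustrative 2 hours at $15 (gross time cost $30.00).

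| Reading | Time cost | Payments entered as explicit cost | Societal total from these two items |
|---|---|---|---|
| Subtract, no other entry | 30.00 − 62.90 = −$32.90 | none | −$32.90 |
| Subtract, and enter as explicit cost | −$32.90 | $62.90 | $30.00 |
| Merely leave payments out of costs | $30.00 | none | $30.00 |

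Under the second reading the total is right. If the $62.90 entry is labelled research and the time is labelled delivery, however, the delivery subtotal is still −$32.90.

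**Step 5. Incremental cost.** The planned 3-month numbers are 240/300, 480/600 and 480/600, which is 80% in every arm. With equal retention and login, the same amount is subtracted per participant in each arm and the difference between arms is unchanged.

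If one arm's retention were higher at every assessment, its extra deduction on the literal reading would be:
- 5 points: 95 × 0.05 = $4.75
- 10 points: 95 × 0.10 = $9.50

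Against an assumed increment of one extra hour at $15, the net increment would be 15.00 − 4.75 = $10.25, or 15.00 − 9.50 = $5.50.

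**The case against.** The strongest defence is that the clause need not mean a bare subtraction. The societal total already takes in all explicit costs. If the incentives are entered there, taking them out of the time value only prevents double counting, and the total equals gross time cost. Alternatively, netting out may simply mean keeping research payments out of the estimate, which would fit the research/delivery labels and the end of payments after the research phase.

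Part of this stands. A reader might infer that the plan flatly contradicts its own societal perspective. The documents support that only on the literal reading, because the other two give a correct total. But no section says that incentives are entered as an explicit cost: the non-labour items named in Section 4.4.2 are materials and supplies, facilities and contracted services. Nor does the sentence say that payments are merely left out. Even the double-counting reading leaves delivery cost too low when the offsetting entry is labelled research.

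A reader might also infer that the rule biases the cost-effectiveness ratio towards the arm with better follow-up. The documents do not project this. The payment schedule is the same in every arm, planned 3-month retention is 80% in each, and the 12-month numbers (154, 307 and 307) keep the 2:2:1 ratio. Section 4.3.1 does hope that UV4.me2's built-in incentives will help retention, so a difference is possible, but neither its presence nor its size is planned for.

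The consequence is also limited. Wage-valued participant time does not enter the payer analysis, and the effectiveness analyses are untouched. The sensitivity analyses in Section 13.2 could vary the value of time, but they would not correct an accounting rule.

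**Conclusion.** The point holds as a statement about the literal rule. It subtracts transfers, 95% of which at the maximum are for surveys, from the opportunity cost of a different activity. The societal time cost, and the delivery cost in each arm, are then understated by about $63 per participant. That figure rests on the planned follow-up, the bonus at its upper bound and 70% login in all arms. The mean net time cost would be negative below roughly 3 to 6 hours of use at an assumed $20 to $10 per hour. Whether actual use falls below that cannot be told from the documents.

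The effect is on cost levels. Incremental cost is unaffected under the plan's equal retention and login. It would shift towards the better-retained arm, by about $4.75 per participant for 5 points at every assessment, only if retention differed and the payments were not also entered as a cost. This concerns a secondary aim. It should be corrected, but it does not touch the primary comparisons.

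**What to change.** In Section 4.4.2 (Cost), delete the clause that nets out incentives. State instead that:
- the societal analysis reports gross wage-valued intervention time;
- research incentives are recorded on a separate research (transfer) line;
- incentives are excluded from intervention-delivery cost in both the payer and the societal analyses.

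Repeat the rule in Section 13.2 (Cost), so that the mean and median costs, the ratios and the scale-up analyses all use the same definition.

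This is a short wording change and needs no new data. The downside is that the reported societal cost per participant becomes less favourable.

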4.5 Compensation

Acceptability/Usability Testing. Participants who complete testing will be eligible to receive \$25 in giftcards or cash equivalent.

RCT. In addition to discounts and free samples, enrolled participants in each intervention condition will be eligible to earn the following incentives in gift-cards or cash equivalent for completing study assessments: 1 month = \$10, 3 months = \$15, 6 months = \$20, 12 months = \$25, plus a \$25 bonus for completing all time-points, and \$5 for logging into the interventions for the first time, for a possible total of \$100 throughout the year, plus a chance in a raffle for \$100 at each time-point. We chose this level of incentives to balance two issues: 1) we wanted to encourage young adults to complete the longitudinal study assessments, but 2) when the research phase is complete, individuals will not be paid for using the program (other than the discounts and free products).

5.0 Risks to Participants

The main potential risks are breach of confidentiality and mild emotional distress. Some participants may become mildly distressed when considering their risk for skin cancer.

6.0 Potential Benefits to Participants

We believe that the UV4.me and UV4.me2 internet interventions may reduce skin cancer risk behaviors among participants and thus ultimately reduce their skin cancer risk.

7.0 Provisions to Maintain the Confidentiality of Data

The data that will be collected will not be sensitive in nature. Therefore, any potential breach of confidentiality would likely not be serious. Research staff will be carefully trained and supervised to maintain confidentiality of data (e.g., by password protecting electronic data). Data collected through the Internet will be obtained through secured means and stored on password protected servers as described above. All data on servers are password-protected and limited to authorized research personnel. This high-level architecture is the same system that has been IRB-approved for use in multiple randomized controlled trials of Internet interventions with which BeHealth has been involved.

Self-report psychosocial data will be collected directly from participants on-line using encrypted and password protected data collection software designed for specifically for that purpose. Password-protected data files will be backed-up onto tape on a daily basis. Data will be maintained in such a way as to facilitate confidential data sharing. Data will be encrypted for transmission. Only members of the research team, all of whom will have been trained in research with human subjects and the importance of

maintaining confidentiality, will have access to the data. The data will be labeled with participant numbers only.

8.0 Costs to Participants

We anticipate no costs to participants during involvement in this research study.

9.0 Consent Process

For the acceptability and usability testing, participants will have an opportunity to read the informed consent and HIPAA documents and review them with a staff member (or others) and ask questions before signing.

For the RCT, participants will be screened, provide consent, and if eligible, complete a survey (< 15 min.) all online. Participants will have an opportunity to read the informed consent and HIPAA documents and review them with a staff member (or others) and ask questions.

10.0 Off-Study Criteria

Based on our data, experience, the enhanced study procedures, and the consumer research panel's experiences with young adults, we anticipate attrition of approximately 20% at each time-point. For dropouts, the reason for attrition will be analyzed if available to search for evidence of informative missingness.

11.0 Drugs and Devices

Not applicable.

12.0 Multi-Site Research Study

Not applicable.

13.0 Statistical Analysis

13.1 Statistical Analyses for Primary Aims

Reach. We will use a one-sample test of a binomial proportion (two-sided, α =0.05) to determine whether the fraction of eligible subjects who enroll and complete the baseline is higher in this project than the prior study. Assuming that 70% of eligible subjects enroll and complete the baseline, we will need access to 2,143 (i.e., 1500/0.70) eligible subjects. Given this sample size, we will be able to detect an increased enrollment and baseline completion proportion with at least 98% power if the true proportion is 70%. Demographic data from enrolled participants will be compared to census data using chi-square goodness of fit tests (two-sided, α =0.05). We will also use the same methods to compare enrollment rates and representativeness separately by recruitment source (i.e., skin protection organizations, Google Adwords, paid Facebook ads, consumer research panel, word of mouth [e.g., unpaid Facebook page, earned media]).

Efficacy. We will compare demographics across randomization arms using chi-squares and ANOVAs for categorical and continuous data, respectively. The primary outcomes are baseline to 3-month changes in UV exposure and protection. We will use multivariable linear regression to compare the effectiveness of UV4.me2 with UV4.me, and UV4.me2 with the e-pamphlet. We will not compare UV4.me to the epamphlet because UV4.me compared to a control condition was established in the prior study. Covariates in these models will include study arm, recruitment month/season, US region, and demographic factors identified as significantly imbalanced across arms (confounders). Analyses will be performed separately for the two primary outcomes. Variance stabilizing transformations may be applied as needed. Hypothesis tests will be two-sided with a 1.25% Type I error to account for multiple testing (2 intervention comparisons x 2 outcomes). Based on our data, experience, the enhanced study procedures, and the consumer research panel's experiences with young adults, we anticipate attrition of approximately 20% at each time-point. With 1500 young adults at baseline, we anticipate collecting 3-month follow-up data from 1200 participants, with 240 from the e-pamphlet arm and 480 participants from each of the other arms. The means (SDs) of the baseline to 3-month changes in UV exposure and protection indexes from the prior study control arm were 0.34 (0.74) and -0.37 (0.90), respectively. Given these parameters, we will have 80% power to detect small standardized effect sizes of 0.22 between the UV4.me2 and UV4.me arms, and 0.26 between the UV4.me2 and the e-pamphlet. These correspond to small detectable differences between intervention arms of 0.16 and 0.19 in baseline to 3-month changes in UV exposure and protection indexes, respectively. We will be able to detect slightly larger differences when the UV4.me2 and e-pamphlet arms are compared (detectable differences - UV exposure: 0.20; protection: 0.24). Analyses will assume that missingness depends on observed data (i.e., missing at random; MAR) 141. For drop-outs, the reason for attrition will be analyzed if available to search for evidence of informative missingness. Baseline variables will be compared by whether participants drop out or not. Significant variables will be added to the model to strengthen our MAR assumption. As a sensitivity analysis, we will use a shared parameter model with the assumption of missing not at random 142. If large changes in parameter estimation are found, we will use the results from the shared parameter model.

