The PI developed a web-based intervention (UV4.me) that was found to significantly decrease UV exposure and increase skin protection behaviors among young adults in a randomized controlled trial (RCT) of nearly 1000 participants recruited from a consumer research panel. The intervention (UV4.me) is individually-tailored, interactive, and multimedia in nature, and based on the Integrative Model of Behavioral Prediction. Similar to other online trials, 73% of eligible individuals completed the baseline questionnaire, 70% who were randomized to the intervention accessed it, and 68% accessed it and completed at least one module. However, we have an opportunity to increase the engagement, implementation, and ultimately, the impact of UV4.me. We will do this by adding several key interactive features/strategies suggested by participants, our data, and supported by the literature (i.e., by creating a mobile version, adding incentives embedded in the intervention, a behavior tracking and feedback feature, peer interaction component, and ongoing news updates). This Hybrid Type 2 dissemination-effectiveness project's purpose is to implement the enhanced intervention (UV4.me2) with adults aged 18-25 years at moderate to high risk of developing skin cancer and evaluate the intervention's effectiveness in a sample recruited online through national dissemination to the general population. This project will use the RE-AIM framework to determine the reach, effectiveness, implementation, maintenance, and cost of UV4.me2.

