2.3 Hypotheses

Hypothesis 1. We hypothesize that the study enrollment rate will be greater than in the original UV4.me efficacy study and that our sample will be representative of national demographics of young adults other than race/ethnicity (associated with skin cancer risk), indicating potential generalizability.

Hypothesis 2. We hypothesize that the UV4.me2 will be the most effective intervention, followed by UV4.me.

Hypothesis 3. We hypothesize that maintenance outcomes will be best in the UV4.me2 group, next best for UV4.me, and least for the e-pamphlet group.

Hypothesis 4. We hypothesize that greater intervention utilization (e.g., logins, module completion) and satisfaction will be associated with better behavioral outcomes

Hypothesis 5. We hypothesize that UV4.me2 and UV4.me will have higher incremental costs than the epamphlet. However, because UV4.me2 and UV4.me are also expected to result in better behavioral outcomes, we will assess cost-effectiveness to address whether these interventions are worth the additional costs.

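### The overall enrolment comparison uses a one-sample test that ignores sampling error in the prior study's rate, so its 5% error and 98% power hold only if that rate is a fixed benchmark

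*Combined protocol and SAP*

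**What the plan says.** Section 2.3 sets the hypothesis: "We hypothesize that the study enrollment rate will be greater than in the original UV4.me efficacy study". Section 13.1 (Reach) gives the method, "We will use a one-sample test of a binomial proportion", two-sided at α = 0.05, and the question it is to answer: "whether the fraction of eligible subjects who enroll and complete the baseline is higher in this project than the prior study". It assumes a current rate of 70%, so that "we will need access to 2,143 (i.e., 1500/0.70) eligible subjects", and claims an increase can be detected "with at least 98% power if the true proportion is 70" per cent. It names no null value.

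The prior rate comes from a "randomized controlled trial (RCT) of nearly 1000 participants recruited from a consumer research panel" (section 1.0). Section 1.0 puts baseline completion among eligible people at 73%. Section 3.0 puts enrolment with baseline completion at about two thirds. Neither section gives the number eligible. Section 13.1 also applies the same methods separately to each of the five recruitment sources, one of which is a consumer research panel.

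**The concern.** The hypothesis and the method do not match. The hypothesis compares two studies, and each supplies an estimated proportion. The one-sample test counts the sampling error of only one of them. Because the prior study probably had fewer eligible people than this one will have, the error left out is larger than the error counted.

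Reach is Primary Aim 1, and this is its overall enrolment test. At stake are a false claim that enrolment improved and a stated power that a comparison of the two studies would not have. The 1,500 target, the randomization and the efficacy tests do not depend on it.

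**Working it through.** **Inputs**

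- From section 13.1: current eligible n1 = 1500/0.70 = 2,143; assumed current rate 0.70; two-sided α = 0.05; stated power at least 98%.
- From sections 1.0 and 3.0: prior rate 73% or about two thirds.
- Assumption: about 1,000 enrolled in the prior study (the text says nearly 1,000). Prior eligible n0 is then 1000/0.73 = 1,370, 1000/(2/3) = 1,500, or 1000/0.66 = 1,515.

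**1. The plan's power.** With a fixed null p0, one-sample power is Φ{[0.70 − p0 − 1.96·√(p0(1−p0)/2143)] / √(0.70·0.30/2143)}.

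- p0 = 0.66: (0.0400 − 1.96 × 0.01023)/0.00990 = 2.01, power 97.8% (exact binomial 97.7%, Wald 98.1%). This reproduces the stated figure. Solving for exactly 98% gives p0 = 0.6596.
- p0 = 2/3: (0.0333 − 1.96 × 0.01018)/0.00990 = 1.35, power 91.2%.
- p0 = 0.73: the assumed 70% lies below the null, so there is no increase to detect.

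The 98% therefore rests on a null of about 66%, a value the documents do not print.

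**2. Error rate when the benchmark is an estimate.** If both studies share one underlying rate, the difference has variance p(1−p)(1/n1 + 1/n0), while the test uses p(1−p)/n1. The standard error is too small by a factor √(1 + n1/n0), and the two-sided error is 2{1 − Φ(1.96/√(1 + n1/n0))}.

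| Prior rate | n0 | n1/n0 | Factor | Two-sided error | Error towards *higher* |
|---|---|---|---|---|---|
| 66% | 1,515 | 1.41 | 1.55 | 20.7% | 10.4% |
| Two thirds | 1,500 | 1.43 | 1.56 | 20.9% | 10.4% |
| 73% | 1,370 | 1.56 | 1.60 | 22.1% | 11.0% |

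Simulation with 400,000 draws per row gave 20.8%, 20.9% and 22.0%. With 950 enrolled instead of 1,000, the two-sided range is 21.4% to 22.8%.

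**3. Power of a two-sample test.** Power is Φ{(0.70 − p0)/SE − 1.96}, with SE = √(0.70·0.30/2143 + p0(1−p0)/n0).

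- p0 = 0.66, n0 = 1,515: SE 0.01569, 0.0400/0.01569 = 2.55, power Φ(0.59) = 72%.
- p0 = 2/3, n0 = 1,500: SE 0.01569, 0.0333/0.01569 = 2.12, power Φ(0.16) = 57%.

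**4. Panel now against panel then.** The panel's share of eligible people is not given. Assuming one fifth to one half of 2,143 (429 to 1,072) and a prior rate of 66% from 1,515, the same formula gives SE 0.0253 to 0.0186 and power of about 35% to 58%. With these smaller samples the one-sample error is also less inflated, at about 8% to 13% two-sided.

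**The case against.** The strongest defence is that testing against a historical rate is a standard benchmark design. If the question is whether this project's fraction differs from a figure already achieved, the 5% is correct. The larger figure answers another question, equality of two underlying rates, averaged over repetitions of a study already finished. This stands as a condition on the result. It does not rescue the plan as written: section 13.1 names no benchmark, the documents report two different prior values, and sections 2.3 and 13.1 both frame the question as this study against the prior one.

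A second objection is that the value of the prior rate matters more than the form of the test. It is fair that no power figure can be relied on until 73% and two thirds are reconciled. But the error rate is 21% to 22% for any of these values, so choosing one does not cure the omission.

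Two stronger readings are tempting.

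- A reader might infer that the enrolment half of Primary Aim 1 has no other formal test. Section 13.1 plans by-source tests as well, and these are less affected.
- A reader might infer that the pooled comparison is invalid because a panel-only rate is set against a mix of five sources. Widening recruitment is part of what Aim 1 sets out to enhance, and by-source analysis is already planned. The documents do not show that the team controls the mix, since it includes outside organizations, earned media and word of mouth. Source mix affects how the pooled difference is interpreted; it is not part of the 21%.

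**Conclusion.** The concern holds for the overall enrolment test, conditionally. Read as a comparison of two underlying rates, the planned test has a two-sided error of about 21% to 22% instead of 5%. For the hypothesis as stated the relevant error is the one towards *higher*: about 10% to 11% against 2.5%. It would be too strong to say without qualification that the test's true error rate is 21%. The figure assumes equal underlying rates and a prior denominator inferred from about 1,000 enrolled, and the 5% holds if the prior rate is read as a fixed benchmark.

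The 98% power depends on that fixed reading and on an unprinted null near 66%. Allowing for the prior study's sampling error, power is about 72% against 66% and about 57% against two thirds. Against 73% no increase could be shown at the assumed 70%. Nothing elsewhere in the documents makes this allowance.

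**What to change.** - Replace the overall one-sample test in section 13.1 with a two-sample comparison of proportions using the prior study's enrolled and eligible counts. Report the difference with its 95% CI.
- Reconcile the prior rate between section 1.0 (73%) and section 3.0 (about two thirds), state both counts, and restate the power for the two-sample test.
- Use the same method for the by-source comparisons already planned. Report the panel-now against panel-then difference with its CI as supportive, and state its lower power.

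The cost is a few sentences and a less favourable stated power. The prior counts should come from the team's own earlier study, so no new data or participants are needed.
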